### **3.3.12.6 Aim 5 (To evaluate pre-post changes in drinking in participants after they receive psilocybin in the third session)**

#### ***3.3.12.6.1 Measures***

The primary drinking outcome for hypothesis 5 is percent heavy drinking days during weeks 39-54 (the 32 weeks following the first drug administration session) as assessed by the Time-line Follow-back [100]. Other drinking variables will serve as secondary outcomes, including percent days abstinent, drinks per drinking day, days to first drinking day, days to first heavy drinking day, and consequences of drinking (from the Short Inventory of Problems [101]).

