
**Aim 1:** To characterize the acute effects of PO psilocybin 25 mg/70 kg, 30 mg/70 kg, and 40 mg/70 kg in alcohol dependent patients: Hypothesis 1: The drug will be well-tolerated, and acute effects will be similar to those observed in normal volunteers.

**Aim 2:** To evaluate the effect of psilocybin treatment on drinking outcomes for 32 weeks after the first administration, relative to diphenhydramine control. Hypothesis 2: A greater decrease in percent heavy drinking days will be observed among participants receiving psychoactive doses of psilocybin in combination with psychosocial treatment than in those receiving diphenhydramine.

**Aim 3:** To test whether or not characteristics of the drug administration session experiences mediate effects of psilocybin on short term (1 week) persisting effects and post-session drinking behavior. Hypothesis 3: Intensity of experience during the drug administration sessions will predict post-session changes in craving, self-efficacy, and motivation, and these changes will in turn predict changes in drinking behavior during the 32 weeks following initial drug administration.

**Aim 4:** To evaluate the explanatory value of changes in alcohol craving, self-efficacy, motivation, and other psychological domains in accounting for the observed experimental effect of psilocybin relative to diphenhydramine control. Hypothesis 4: Changes in craving, self-efficacy, and motivation will mediate the effects of psilocybin treatment on drinking behavior.

**Aim 5:** To evaluate pre-post changes in drinking in participants after they receive psilocybin in the third session. Hypothesis 5: participants in the control group will show decreases in drinking during the 16 weeks following the psilocybin session at week 38.

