##### ***3.3.8.1.3 Dosing and Administration of Study Medications***

Setting. The psilocybin sessions will take place in outpatient facilities that are appropriate for hallucinogen administration sessions. To the extent possible, the room used for the session will be specially prepared for the sessions to provide a warm and home-like rather than a stark clinical quality because of the large influence that setting can have on the subjective effects of hallucinogens. Each site will have detailed SOPs in place for managing medical or psychiatric emergencies should any occur.

Safety Screening on the Day of Drug Administration Sessions. Participants will be required to attempt to remain abstinent during the week preceding the drug administration sessions. On the morning of the psilocybin session, participants must have a negative breathalyzer reading, drug screen must be negative for all non-prescribed tested drugs of abuse except for marijuana, CIWA-Ar score must be less than 8, and vital signs must be within normal limits (afebrile, blood pressure less than or equal to 140 systolic, 90 diastolic, resting pulse less than 100). Female participants of childbearing potential must also have a negative urine pregnancy test.

Dosing of Study Medications. Individualized doses of psilocybin will be prepared by the site pharmacist using an analytical balance. Medication will be placed in an opaque gelatin capsule prior to administration, with the balance of the capsule volume filled with microcrystalline cellulose.

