### 3.3.10 Measures

Measures are listed in Table 1 below, organized by domain.

Table 1. Assessment Schedule		Scr.	BL	W04	W05	W08	W09	W12	W24	W36	W38	W39	W42	W54
Medical evaluation	History and physical, liver function tests, complete blood count, Chem 7, U/A, serum pregnancy test, height and weight, medical history intake form	550'												
	ECG		5'							5'				
	Concomitant meds, menstrual calendar		5'	5'	5'	5'	5'	5'	5'	5'	5'	5'	5'	5'
	Urine pregnancy test				5'		5'				5'			
Psychiatric and SUD assessment	Structured Clinical Interview for DSM-IV (SCID), Family History Questionnaire, Folstein MMSE	75'												
Other baseline characteristics	Attentional Resource Allocation Scale, Treatment Goal Form, Demographics Form, Locator Form			15'										
Withdrawal	CIWA-Ar	5'		5'		5'					5'			
Substance use and consequences	Time-line Follow-back, BAC	30'	10'	10'		10'		10'	10'	10'	10'		10'	10'
	Hair/ Nail sample for ethyl glucuronide									5'				
	Urine Drug Screen	5'		5'		5'		5'	5'	5'	5'		5'	5'
	Short Inventory of Problems (past 3 months)		5'					5'	5'	5'				5'
Acute Hallucinogen Effects	5D-ASC, HRS, SCQ, Monitor Rating Scale, Mysticism scale, guesses of medication received, MUSE questionnaire			30'		30'					30'			
Persisting Effects	Mysticism Scale (lifetime), Spiritual Transcendence Scale, Persisting Effects Questionnaire (follow-up)		90'							90'				90'

	only), BMMRS, NEO-PI-3, Schwartz Value Survey													
Motivation	Readiness rulers		5'	5'	5'	5'	5'	5'	5'	5'	5'	5'	5'	
Self-efficacy	Alcohol Abstinence Self-efficacy Scale		10'	10'	10'	10'	10'	10'	10'	10'	10'	10'	10'	
Craving	Penn Alcohol Craving Scale		5'	5'	5'	5'	5'	5'	5'	5'	5'	5'	5'	
Self-Compassion	Self-Compassion Scale (Short Form)		5	5	5	5	5	5	5	5	5	5	5	
Mood/ Anxiety	Ham-D, Ham-A		20'	20'	20'	20'	20'	20'	20'	20'	20'	20'	20'	
	Adverse Events Case Report Form			5'	5'	5'	5'	5'	5'	5'	5'	5'	5'	
Safety	Vital Signs and weight	5'	5'	5'	5'	5'	5'	5"	5'	5'	5'	5'	5'	
	Visual Analog Scales for abuse potential							5'	5'	5'			5'	
Tx satisfact.	Visual Analog Scales							5'					5'	
Assessment Length		185'	175'	110'	55'	110'	55'	85'	85'	170'	110'	55'	75'	170'

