### 3.3.12.3.2 Method

For PHDD we will employ a MMRM including fixed, categorical effects of treatment, assessment, and site; site-by-treatment and treatment-by-assessment interactions; the continuous, a fixed covariate (week 1-4 PHDD); and using monthly values of PHDD (weeks 5-8, 9-12, 13-16, 17-20, 21-24, 25-28, 29-32, 32-36) as the dependent measure. Site and the site-by-treatment interaction will be removed from the final model if not significant at the  $p < 0.05$  level. Secondary drinking measures with a continuous scale of measurement, i.e., PDA and DPDD, will be tested in a similar fashion and for days to first drinking day and days to first heavy drinking day (5 or more standard drinks for a man, 4 or more standard drinks for a woman). Cox survival analysis will be used. Measures of effect size will be calculated for all planned between-group contrasts (Hedges  $d$ ) and the  $Q$  statistic will be calculated to assess the homogeneity of effect across the primary and secondary outcome measures of drinking.

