#### ***3.3.12.6.2 Method***

Methods for Aim 5 will parallel those used in Aim 2, except that only participants in the control group will be included in this analysis, so treatment and site-by-treatment interactions will be omitted from the model, with the time effect being of principal interest. PHDD will be centered at week 42.

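### Aim 5 asks for a pre-post change, but its outcome and principal time effect cover only weeks after the third session, and the window is mislabelled

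*Combined protocol and SAP*

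**What the plan says.** Section 2 (Specific Aims) gives Aim 5 as "To evaluate pre-post changes in drinking in participants after they receive psilocybin in the third session". Hypothesis 5 adds that "participants in the control group will show decreases in drinking during the 16 weeks following the psilocybin session at week 38".

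Section 3.3.12.6.1 makes the outcome "percent heavy drinking days during weeks 39-54 (the 32 weeks following the first drug administration session" (the bracket closes there). Section 3.3.12.6.2 says the methods follow Aim 2, restricted to the control group and without the treatment terms, "with the time effect being of principal interest. PHDD will be centered at week 42".

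The Aim 2 template in section 3.3.12.3.2 uses "monthly values of PHDD (weeks 5-8, 9-12, 13-16, 17-20, 21-24, 25-28, 29-32, 32-36) as the dependent measure". All of these months follow the first session. Drinking before that session enters only as "a fixed covariate (week 1-4 PHDD".

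Section 3.3.12 refers to the SAP for the full analyses. No SAP text on Aim 5 was available for this review, so the point concerns the protocol's wording.

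**The concern.** The aim and the test do not match. A pre-post question needs a pre-session value to compare against, and Aim 5 names none, either as an outcome level, as a comparator or as its covariate. The only reference point given, week 42, is the end of the first post-session month.

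In Aim 2 the lack of a pre-session level does no harm, because the randomised treatment effect carries the inference. Once treatment is removed, the time effect is all that remains, and it asks only whether post-session months differ from each other. The result that Hypothesis 5 hopes for, a drop at week 38 that lasts, would usually give a null test. A benefit that wears off could give a significant test in the wrong direction.

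The bracketed gloss on the window is Aim 2's description of weeks 5-36, which suggests that the text was carried over without full adaptation.

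**Working it through.** **Window.** Counting inclusively, weeks 5-36 are 36 − 5 + 1 = 32 weeks, which fits the gloss for Aim 2. Weeks 39-54 are 54 − 39 + 1 = 16 weeks, or four 4-week months, starting after the week-38 session. The 16 weeks agree with Hypothesis 5 and section 3.3.1. No choice of anchor makes weeks 39-54 the 32 weeks after the first session.

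**What the time effect tests.** Let μ0 be mean percent heavy drinking days (PHDD) before the session and μ1 to μ4 the means of the four post-session months. The post-only time effect tests μ1 = μ2 = μ3 = μ4, and μ0 does not appear. For a sustained fall of size δ, every μj = μ0 − δ, so all differences between post-session months are zero. The noncentrality is zero and the rejection rate is 5% for any δ, n, SD or correlation.

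**What a pre-post contrast tests.** The contrast is D = (μ1+μ2+μ3+μ4)/4 − μ0. The protocol gives no PHDD variance and no power statement for Aim 5, so these inputs are assumptions: n = 50-85 controls analysed (of 90 assigned), SD 25-35 points, correlation between months 0.5-0.7, either constant or decaying as AR(1).

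- With constant correlation ρ, Var(D) per person = SD²(1 − ρ)(1 + 1/4). For SD 25 and ρ = 0.6 this is 625 × 0.4 × 1.25 = 312.5. With n = 85, SE = √(312.5/85) = 1.92. A 10-point fall is 10/1.92 = 5.2 standard errors, and power is 99.9%.
- The least favourable cell is n = 50, SD 35, AR(1) with 0.5. The mean of the four months has variance (4 + 2(3×0.5 + 2×0.25 + 0.125))/16 = 0.516 SD². Its covariance with the pre-session month is (0.5 + 0.25 + 0.125 + 0.0625)/4 = 0.234 SD². So Var(D) = (1 + 0.516 − 0.469) × 1225 = 1,282 and SE = √(1282/50) = 5.06. A 10-point fall is 1.97 standard errors, and power is 49%.

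**Simulation over the full grid** (36 combinations, 2,000 runs each). The categorical test is a Hotelling test of equal post-session months; the linear test is a slope over those months.

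| True pattern | Time effect, categorical | Time effect, linear | Post minus pre |
|---|---|---|---|
| Sustained 10-point fall | 4.0-5.8% | 4.0-6.3% | 51-100% |
| Sustained 20-point fall | 3.8-6.0% (both codings) | 3.8-6.0% (both codings) | 98-100% |
| 15-point fall fading to 0 by month 4 | 43-100% | 59-100% | – |

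The simulated lower end of 51% agrees with the calculated 49% within simulation error. In the fading pattern the slope was upward in essentially every significant run.

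**Covariate.** A value that is constant within a person shifts the level of all post-session months equally and leaves their differences alone. Mixed-model fits (n = 70, 15% dropout, sustained 10-point fall, 300 fits) rejected in 4.7% with weeks 1-4 as covariate, 4.3% with weeks 33-36 and 5.3% with none. The Monte Carlo standard error is √(0.05×0.95/300) = 1.3 points, so all three are consistent with 5%.

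**Bounded outcome.** With counts of days out of 28, an assumed pre-session mean of 40% and n 50-85, sustained falls of 10-20 points gave 4.4-5.4% for the time effect against 92-100% for post minus pre.

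**The case against.** The strongest reply is that section 3.3.12.6.2 is brief rather than wrong. It does not list the levels of time; the section heading itself says pre-post; and treatment may have been dropped so that time could carry the before-after comparison. The SAP may spell this out. That possibility stands, and it is why the point is limited to the protocol. But the protocol does state an outcome window (weeks 39-54) and a template (post-session months as the dependent measure), and together these exclude a pre-session level.

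Hypothesis 5, read alone, could mean a decline within the 16 weeks, which a post-session time effect would test. The wording of the aim outweighs that reading.

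If the covariate were drinking just before week 38, the fitted post-session level could be compared with the baseline mean. That is so, but it would be a different test from the time effect named as principal, and the protocol does not say which covariate applies. The sentence on centring is also ambiguous, since it says that PHDD, not time, is centred.

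The power figures for the contrast and the single fading shape rest on assumptions. The 5% rate under a sustained fall does not. Finally, Aim 5 is optional, open-label, uncontrolled and not powered, and the printed week numbers limit the harm from the wrong gloss. This bears on priority, not on whether the text needs correction.

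**Conclusion.** The point holds for the protocol as written. The principal Aim 5 test does not address the stated pre-post change. Under a sustained fall of any size it rejects at about 5%, whatever the sample size, variance or correlation. Over the assumed ranges, a post-minus-pre contrast would have power of about 49-100% for a 10-point fall. Under the one fading pattern examined, the time effect is significant in 43-100% of runs, and the direction is an increase in drinking. The gloss on the window is wrong in both length (16 weeks, not 32) and anchor (third session, not first).

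This should be fixed before analysis. It affects Aim 5 only; the primary outcome under Aim 2 is untouched.

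**What to change.** 1. In section 3.3.12.6.1, describe weeks 39-54 as the 16 weeks after the third drug administration session.
2. In section 3.3.12.6.2, for control participants who received that session, add a pre-session interval as a level of the repeated measure. Weeks 33-36 is a natural choice: it is the last Aim 2 month (printed there as 32-36, which overlaps the month before and should also be corrected).
3. Make the principal Aim 5 test the contrast of mean PHDD over weeks 39-54 minus that interval, with the trend across post-session months secondary.
4. State which covariate is used, if any, and whether time is categorical or continuous, and clarify what is centred at week 42.
5. Report the result as an uncontrolled pre-post comparison, and check that the SAP agrees.

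Weeks 35-38 would parallel Aim 2's weeks 1-4, but section 3.3.8.1.3 says "Participants will be required to attempt to remain abstinent during the week preceding the drug administration sessions". If week 38 were wholly abstinent, 7/28 = 25% of the baseline days would be zero, and a true PHDD of 20-50% (assumed) would be understated by 5 to 12.5 points. This is an upper bound, since only an attempt is required. Aim 2's covariate has the same feature, but there both arms share it.

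The cost is wording in the protocol, and in the SAP if it repeats this text. No new data are needed: Table 1 in section 3.3.10 schedules the row "Time-line Follow-back, BAC" at weeks 36, 38, 42 and 54, which covers both intervals.

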#### ***3.3.12.6.2 Method***

Methods for Aim 5 will parallel those used in Aim 2, except that only participants in the control group will be included in this analysis, so treatment and site-by-treatment interactions will be omitted from the model, with the time effect being of principal interest. PHDD will be centered at week 42.

#### **3.3.12.7 Statistical power**

Power analysis is based on the primary outcome analysis contrasting the psilocybin group with the control group with respect to percent heavy drinking days in months 1-8 post pharmacologic treatment (Aim 2). With a total sample size of  $n = 180$  (90 assigned to psilocybin and 90 to control), and 5% attrition (realistic because useable data require only 1 month follow-up in participants who have already participated for 1 month,  $N = 171$ ) our power analysis was based on the assumption that four predictors would be in the regression-based HLM model. We estimate that the study has power of 0.8 to detect an effect of size  $f^2 = .065$ , with alpha = 0.05 (2-tailed) and no correction for multiple comparisons. This effect is comparable to that of naltrexone [9, 158, 159], and smaller than those observed in some recent trials of other promising medications [160-162]. Regardless of the statistical significance of these changes, standardized and non-standardized effect sizes will be computed for primary and secondary outcome variables. The addition of an open-label optional third dosing does not affect the required sample size for Aim 2 (primary outcome), but approximately doubles the sample size for Aim 1 and allows for the addition of Aim 5.

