### **3.3.12 Statistical analysis and power**

A full description of the planned analyses for this trial can be found in the Statistical Analysis Plan (SAP)

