#### 3.3.12.4.2 Method

Tests of statistical mediation will use a product-of-coefficients approach with a bootstrapping procedure. This choice provides the most powerful test of mediation with smaller samples and does not assume normality in the distribution of ( $a'b'$ ) product terms (Preacher and Hayes, 2008; Hayes, 2009). HLM will be applied to identify the  $a$  and  $b$  parameter estimates for the between-group contrast (treatment assignment psilocybin versus control;  $df = 1$ ), and baseline values of the dependent variable will be entered in level 2.

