#### **3.3.13 Study Milestones**

We propose to implement the study in three stages, with interim analyses and DSMB review after the first and second stages.

Stage 1: Following final protocol approval by all necessary authorities and procurement of necessary funding, staff will be trained, at least 4 pilot/training participants per site will be treated, and 20 participants will be randomized into the main trial across two sites (UNM and NYU, 10 per site). At the end of this stage, feasibility and tolerability will be assessed, and necessary protocol modifications may be made.

Stage 2: An additional 80 participants will be randomized, with the possible addition of one or two additional sites to enhance recruitment capacity. At the end of this stage, interim checks of attrition rates and the assumed error standard deviation  $\sigma$  for the primary outcome measure will be conducted to assess the adequacy of the projected study sample size. This check will be performed by an unblinded statistician, who will estimate the primary model, and report back on error variance and drop-out rates. Additional necessary protocol modifications may be made, and final sample size will be determined. In addition, safety interim looks will be performed (without formal statistical testing) at the regular DSMB meetings or unscheduled times per the DSMB's request. Although at this time we are not planning a formal statistical interim analysis for efficacy or futility, such an interim analysis can be performed if requested by the DSMB or the sponsor.

Stage 3: Assuming 180 participants are required, the 80 remaining participants will be randomized, with an additional 9 months to complete treatment and assessment of the final participants.

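### The power statement (80% at f² = .065) does not fit the two-arm contrast it names: the same inputs give 91% power, and 80% power is reached at f² = 0.046

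*Combined protocol and SAP*

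**What the plan says.** Section 3.3.12.7 ties the calculation to the primary comparison: "Power analysis is based on the primary outcome analysis contrasting the psilocybin group with the control group", for PHDD over the eight months after the first drug session. Its inputs are 180 randomized (90 per arm), 5% attrition leaving N = 171, two-tailed alpha of 0.05 and no multiplicity correction. On the model it says that "our power analysis was based on the assumption that four predictors would be in the regression-based HLM model". The result is "We estimate that the study has power of 0.8 to detect an effect of size" f² = .065, which it then likens to the effect of naltrexone.

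The section does not give the numerator degrees of freedom or say how many of the four predictors are tested. Elsewhere the comparison is a single one:

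- Hypothesis 2 (section 2) predicts that "A greater decrease in percent heavy drinking days will be observed among participants receiving psychoactive doses of psilocybin" than among those given diphenhydramine.
- Section 3.3.12.4.2, on the Aim 3 mediation analysis, refers to "parameter estimates for the between-group contrast (treatment assignment psilocybin versus control" and assigns it df = 1.
- Section 3.3.12.3.2 specifies a repeated-measures model over eight four-week periods. There, treatment is a two-level factor (1 df) and treatment-by-assessment has (2 − 1) × (8 − 1) = 7 df.

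**The concern.** A power figure belongs to a particular test. The test named here has 1 df, and 80% power at f² = .065 with 171 participants looked too low for it.

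This is the only sensitivity statement for the primary analysis in the supplied text. If it is wrong for the named contrast, a reader will take the smallest effect detectable with 80% power to be larger than it is. That affects how a null or small result is read against the design, and it affects the comparison with naltrexone, which is attached to the .065 figure. Section 3.3.13 also plans, after Stage 2, "interim checks of attrition rates and the assumed error standard deviation" to judge whether the projected sample size is adequate. That judgement needs a detectable effect that belongs to the primary test.

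**Working it through.** **Inputs, all from section 3.3.12.7 unless noted**

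- Analysable N: 180 × 0.95 = 171, as printed.
- Predictors in the model: p = 4, so denominator df v = 171 − 4 − 1 = 166.
- f² = .065; alpha = 0.05 two-tailed, uncorrected.
- Numerator df u: not stated. For two arms, u = 1, which agrees with the df = 1 in section 3.3.12.4.2.

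**Formula.** Power = P[F′(u, v, λ) > F(0.95; u, v)], where F′ is the noncentral F distribution and λ = f² × N = 0.065 × 171 = 11.1. This treats each participant as one observation and assumes that f² is carried by the tested term or terms.

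**Trying to reproduce the printed pair (0.8 at .065)**

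| Numerator df u | Power at f² = .065 | f² at 80% power |
|---|---|---|
| 1 | 0.912 | 0.0464 |
| 2 | 0.850 | 0.0574 |
| 3 | 0.798 | 0.0653 |
| 4 | 0.754 | 0.0718 |

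The printed pair reproduces only at u = 3. It does not reproduce for a two-arm contrast (u = 1) or for a joint test of all four predictors (u = 4).

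**Is the 1-df result sensitive to the other inputs?**

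- Number of predictors: power is 0.912 with anything from 1 to 20 in the model, so the four-predictor assumption does not account for the gap.
- Noncentrality convention: λ = f² × (u + v + 1) = 0.065 × 168 = 10.9 gives 0.9075, with 80% power at f² = 0.0473. λ = f² × v gives 0.904.
- No attrition (N = 180): 0.925.
- Two-sample t test with 85.5 per arm and d = 0.51: 0.912.
- Alpha of 0.0125 with 1 df: 0.79, close to the printed figure, but the section says no correction was applied.
- Analysable N needed for 80% power at f² = .065 with 1 df: 123, against 171 available.

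**Converting to a difference between arms.** For two equal groups, d = 2√f².

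- As printed: 2 × √0.065 = 0.51.
- For the 1-df contrast: 2 × √0.0464 = 0.43.
- Ratio in f²: 0.065 / 0.0464 = 1.4.

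The supplied text gives no residual SD for PHDD. Over an assumed range, the difference detectable at 80% power (d × SD) is:

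| Assumed residual SD (PHDD points) | As printed (d = 0.51) | 1-df contrast (d = 0.43) |
|---|---|---|
| 20 | 10.2 | 8.6 |
| 25 | 12.7 | 10.8 |
| 30 | 15.3 | 12.9 |

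**The case against.** The strongest reply is that this is an unstated degree of freedom rather than faulty arithmetic. Section 3.3.12.7 never gives the numerator df, and 3 df recovers the printed pair almost exactly. A 3-df origin can be imagined: with two sites, the between-person part of the primary model has four coefficients (baseline PHDD, treatment, site, site-by-treatment), and three remain once the covariate is set aside. The explicit df = 1 comes from the Aim 3 method, not from Aim 2.

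The 3-df match stands, and it is probably where the figure came from. It does not rescue the sentence. No section describes such a test, a joint test that includes site is not a comparison of psilocybin with control, and the stated two-tailed alpha also points to a single coefficient.

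A second reply is that the planned analysis is a repeated-measures model, so 0.91 is not its power either. That also stands as a limit. No SD or within-person correlation is supplied, so the power of that model cannot be recomputed. The finding concerns the protocol's own f² calculation on 171 participants and says nothing beyond it.

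Finally, the consequence is modest. The error is conservative, the result will be read from its estimate and interval, and Stage 2 includes a sample-size check. This limits the weight of the point but does not make the printed figure right for the contrast it names.

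**Conclusion.** The concern holds. For the psilocybin-versus-control contrast, on the inputs printed in section 3.3.12.7, power at f² = .065 is 0.91 rather than 0.80. The effect detectable with 80% power is f² = 0.046 (d about 0.43) rather than .065 (d about 0.51). Power is understated by 11 points, and the detectable effect is overstated 1.4-fold in f².

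This rests on three things: a 1-df test, the participant as the unit of analysis, and f² carried by the treatment term. It is insensitive to the number of predictors and to the noncentrality convention (0.904 to 0.912). The error is in the safe direction and gives no ground for changing n = 180.

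**What to change.** Restate the result in section 3.3.12.7, for example: *With 171 analysable participants (participant as unit), the 1-df treatment contrast has 80% power for f² = 0.046 (d about 0.43 in residual-SD units) and 91% power for f² = .065.* The comparison with naltrexone should then be checked against whichever figure is kept as the detectable effect.

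If a joint test of several terms was intended, keep the printed figures but name those terms and their degrees of freedom, and stop describing the calculation as the two-arm contrast.

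The cost is a wording change in the protocol, carried into the SAP if the statement is repeated there. Sample size, design and analysis are unchanged.
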